7.4.4.5 Ocular surface staining

Fluorescein (TF) staining: A drop of topical anesthetic will be instilled in the bottom of the conjunctival sac, then a second drop will be applied to the tip of the fluorescein strip, allowing it to sit on the strip for 5 seconds to elute the dye, shaking off the excess at the end. A small contact of the strip is made with the conjunctiva at the fundus of the temporal sac, while the subject looks upwards, without damaging the conjunctiva. Between 4 and 8 minutes after the instillation of the staining, the assessment of the fluorescein stain in the cornea is carried out, with the slit lamp with a cobalt blue filter. It will be graded according to the Oxford Scale. See attachment [41, 42][16.3 Oxford scale](#)

The PI will record in the file and the eCRF the grade, in grades (Grade 0 = Absent, grade I = Minimal, grade II = Mild, grade III = Moderate, grade IV = Marked, grade V = Severe), granted for the corneal staining of OD and OS respectively.

Management as AE: An adverse event will be considered when the rating is greater than or equal to grade III (moderate).

7.4.4.6 Adverse events

As described in the [8. Evaluation and management of adverse events](#) An adverse event is defined as any unfavorable medical occurrence in a subject to whom an investigational product is administered, regardless of causal attribution.

Adverse event management shall be carried out as described in section [8. Evaluation and management of adverse events and incidents](#).

The Principal Investigator will record in the corresponding section of the eCRF the adverse events that the study subjects may present in addition to referring them in the clinical record.

For an adequate evaluation of adverse events, in addition to directed questioning, it is necessary to perform a comprehensive ophthalmological evaluation at each visit, which consists of: ophthalmological examination of the eyelids and adnexa; anterior and posterior segment that is performed in a routine ophthalmological check-up, whose procedures are not specifically included in the study variables. Posterior pole evaluation can be with direct or indirect ophthalmoscopy, with or without pharmacological mydriasis, at the discretion of the PI. An assessment of the fundus will be carried out in search of abnormalities that alter the result of the study. IOP will be measured in this evaluation, with the Goldmann tonometer, it should be measured after the evaluation of stains. The result of the assessment will be recorded in the clinical file. In the eCRF, only findings that are considered so by the Principal Investigator will be reported as an adverse event.

The ocular adverse events that can occur with PRO-231, according to what is reported in the literature, are: ocular burning, dysgeusia after instillation, foreign body sensation, ocular pruritus, conjunctival hyperemia, chemosis, photophobia and whitish corneal precipitates. The frequency of systemic adverse events with ophthalmic fluoroquinolone administration is low.[\[1, 13\]](#) [\[1\]](#)

7.4.4.7 Eye Comfort Index

It is a questionnaire designed to measure ocular surface irritation with Rasch analysis to produce estimates on a linear interval scale (ratings: 0-100). Similar to the index for ocular surface diseases, the ocular comfort index (ICO) assesses symptoms. The ICO contains 8 items (one positive and eight negative) that focus on discomfort associated with ocular surface alterations. Each of these questions has two parts, which separately inquire about the frequency and severity of symptoms. [\[43\]](#) See attachment [16.4 Eye Comfort Index \(JI\)](#)

At the baseline visit and final visit, the evaluator will deliver the questionnaire to the subject and allow the subject to answer it calmly without any pressure and/or coercion, only assisting him if he has difficulty understanding any of the questions.

As it is a subjective measurement scale according to the subject's symptomatology, variations in the ICO cannot be managed as AEs.

7.5 Description of procedures or assessments during the study

The different procedures that will be done during the study are described below. The list may not be in order, and it may be arranged in the most optimal way according to the needs of the research center.

7.5.1 Signing of informed consent

Procedure by which it is guaranteed that the subject under investigation has voluntarily expressed his intention to participate in this research, after having understood the information that has been given to him about the objectives of the research, benefits, discomforts, and possible risks.

7.5.2 Preparation of medical history (includes ophthalmological and general medical history)

It must be carried out in accordance with the provisions of NOM-004-SSA3-2012 of the clinical file. Considering that the clinical record is the unique set of information and personal data of a subject, which is integrated into any type of establishment for medical care, whether public, social or private, which consists of written, graphic, imaging, electronic, magnetic, electromagnetic, optical, magneto-optical and any other type of documents, in which, Health personnel must make the records, annotations, where appropriate, certificates and certifications corresponding to their intervention in the subject's medical care, in accordance with the applicable legal provisions. [44]

And it will consist of:

- Medical history: It must be prepared by medical personnel and other professionals in the health area, in accordance with the specific information needs of each of them in particular, it must have, in the order indicated, the following sections:
 - Interrogation. – It must have at least: identification form, if applicable, ethnic group, hereditary-family history, pathological and non-pathological personal history, current condition (inquire about previous conventional, alternative and traditional treatments) and interrogation by devices and systems (especially ophthalmological).
 - Physical exam. – You must have at least: vital signs (temperature, blood pressure, heart and respiratory rate), weight and height (when applicable).
 - Previous and current results of laboratory, cabinet and other studies (when applicable).
 - Diagnoses or clinical problems (when applicable).
 - Prognosis (when applicable).

- Therapeutic indication (when applicable).

7.5.3 Eligibility Criteria

It is the assessment that the subject meets all the inclusion criteria and none of the exclusion or elimination criteria.

7.5.4 Assigning Subject Code

It is the granting of a code that represents the subject in the study. This code is assigned when the research subject is included in the study.

7.5.5 Adverse events

Described in the [8. Evaluation and management of adverse events](#)

7.5.6 Vital Signs Measurement

It is the measurement of respiratory rate, heart rate and blood pressure. These measurements can be made with a stethoscope and mercury or digital sphygmomanometer.

7.5.7 Urine Pregnancy Test

The pregnancy test will be performed at the baseline visit and at the final visit. The Researcher must provide the research subject with a female, of reproductive age (there is no natural or induced menopause, defined as 12 consecutive months of amenorrhea). Women of childbearing potential with contraceptive methods including bilateral tubal obstruction should take a pregnancy test. To perform the test, the subject will be allowed to go to the bathroom, have privacy for the performance of the test, and after the test is performed, the Investigator must corroborate the result by observing the medical device. [45]

7.5.8 Ophthalmological evaluation

Evaluation of your eyeball, eyelids, eyelashes, and other structures of your eyes by inspection, slit lamp (biomicroscopy), as well as palpation (touch). As part of this evaluation, visual acuity is taken with better corrected visual acuity, the integrity of the ocular surface is assessed, the anterior segment, intraocular pressure is taken, gonioscopy is assessed, and posterior segment (fundoscopy) is assessed.

7.5.8.1 Best-corrected visual acuity

Described in the [7.4.4.4 Best-corrected visual acuity](#)

7.5.8.2 Ocular Surface Integrity

This will be done by means of biomicroscopy using the slit lamp of the research center. An inspection of the cornea, conjunctiva, tear film, and fluorescein eye staining will be done (in section [7.4.4.5 Ocular surface staining](#)).

7.5.8.3 Previous segment

It is the evaluation of the structures of the anterior segment (cornea, conjunctiva, anterior chamber, iris, pupil, lens, aqueous humor). The evaluation will be made by means of the slit lamp.

7.5.8.4 Intraocular pressure

Tonometry is the objective measurement of IOP, based primarily on the force required to flatten the cornea or the degree of corneal indentation produced by a fixed force. Goldmann tonometry is based on the Imbert-Fick principle. [46]

The tonometry will be performed with a Goldmann tonometer, after instillation of the topical anesthetic, with fluorescein and the use of the cobalt blue filter (after the evaluation of the surface staining). 2 samples will be taken and the average will be calculated, which will be recorded in the clinical file.

7.5.8.5 Gonioscopy

It is the assessment of the iridocorneal angle by attaching a gonioscopy lens to the subject's cornea. In some cases the lens will be filled with a high viscosity solution (2% hypromellose) to improve the coupling of it with the subject's cornea.

This evaluation will be carried out only at the baseline visit as part of the comprehensive ophthalmological check-up and will be useful to corroborate the subject's ophthalmological health status.

For the classification of the angle, the Shaffer system will be used.

Board 3. Shaffer's classification

DEGREE	ANGLED APERTURE	DESCRIPTION	RISK OF OCCLUDING
4	45°-35°	Open	Impossible
3	35°-20°	Open	Impossible
2	20°	Narrow	Possible
1	≤ 10°	Extremely narrow	Probable
0	0°	Closed	Occluded

Angular closure or suspected angular closure shall be considered to be Grade 2 or less in more than 180° of the angular circumference.

7.5.8.6 Posterior Segment (Fundoscopy)

Also called ophthalmoscopy. This is the test done with a light and a magnifying glass to look at the fundus (optic nerve and retina) through the pupil. Sometimes the pupil will need to be dilated so that the fundus of the eye can be fully evaluated.

This evaluation will be carried out only at the baseline visit as part of the comprehensive ophthalmological check-up under pharmacological mydriasis and will be useful to corroborate the subject's ophthalmological health status.

7.5.9 Application of Medications During Visits

During the visits to the subjects, different medications or medical devices may be applied to the ocular surface for ophthalmological examination.

Examples:

- Tetracaine 0.5% ophthalmic solution, used to anesthetize the subject's ocular surface and facilitate the measurement of intraocular pressure, application of dyes for stains and placement of the lens for gonioscopy.
- Ophthalmic solution of tropicamide 0.8% and phenylephrine 5%, used to dilate the pupil and better assess the posterior segment.
- Hypromellose ophthalmic solution 2%, may be used by the Investigator for the assessment of gonioscopy.

7.5.10 Delivery of material for the subject

It refers to the delivery of the subject's identification card and the subject's diary. The ID card will serve as an ID with the treatment assignment number, this card may serve as an appointment card. The Subject's Diary serves to keep track of the times the treatment is applied.

7.5.11 Delivery of Study Medication

Once the subject is in the study, the investigational product will be given, and the dosage of the product will be explained (one drop three times a day in the right eye).

7.5.12 Evaluation of concomitant medicinal products

It is the question about the use of medications that they are taking regularly or that they have used in the last month. If you have required injected eye drug therapy, you should ask about the injected drugs in the last 6 months.

7.5.13 Assessment of adherence to treatment

It refers to indirectly evaluating the number of applications during the period between visits. In order to assess the approximate number of drops, the Subject's Journal can be reviewed to find out the applications registered.

7.5.14 Return of Study Medication

It refers to the return made by the research subject of the product under investigation.

7.5.15 Subject Journal Removal

It refers to the delivery made by the research subject of the subject's diary.

7.6 Study Diagram and Timeline

7.6.1 Study diagram

[figure not shown]

Figure 2. Study diagram

7.6.2 Study timeline

Procedures	Scrutiny / Basal Visit	Visit 1	Final Visit	Call Security
	Day 0	Day 3 ± 1	Day 8	Day 12 ± 1
Signing the informed consent form	X			
Medical history	X			
Ophthalmological medical history	X			
Urine pregnancy test	X		X	
Eligibility Criteria	X			
Eye symptoms	X	X	X	
AVMC Measurement	X	X	X	
Previous Segment Evaluation	X	X	X	
Fluorescein staining evaluation	X	X	X	
Intraocular pressure measurement	X	X	X	
Posterior Segment Evaluation	X		X	
Subject and IP code assignment	X			
Delivery of the PIs and indicate the start of application the next day (day 1)	X			
Return of IP			X	
Adherence assessment		X	X	
Evaluation of adverse events	X	X	X	X
Eye Comfort Index	X		X	
Subject Diary Delivery	X			
Return / Evaluation of the subject's Journal			X	
Subject continuity assessment		X		

Abbreviations: AVMC, best corrected visual acuity; PI, research products.

Board 4. Study timeline

7.7 Procedures to be carried out per visit

Listed below are the procedures that will be performed at each visit, which may not show the optimal order for the Research Center. The investigator should order it according to his or her needs, and the needs of the study and sponsor.

In the evaluation of adherence to treatment, it can be reviewed in the subject's diary.

7.7.1 Baseline visit

- Signing of informed consent
- Preparation of general and ophthalmological medical history
- Pregnancy test (where applicable)
- Best-corrected visual acuity measurement
- Previous Segment Evaluation
- Fundus evaluation under pharmacologic mydriasis
- Evaluation of the angle in the anterior chamber (gonioscopy)
- Fluorescein Eye Staining
- Intraocular pressure measurement
- Evaluation of adverse events
- Eye symptoms
- Eye Comfort Index (ILO)
- Subject Code Assignment and Research Product Delivery
- Submission of the subject's diary

7.7.2 Visit 1

- Best-corrected visual acuity measurement
- Previous Segment Evaluation
- Fluorescein Eye Staining
- Intraocular pressure measurement
- Evaluation of adverse events
- Adherence Assessment
- Eye symptoms

7.7.3 Final Visit

- Pregnancy test (where applicable)
- Best-corrected visual acuity measurement
- Previous Segment Evaluation
- Posterior Segment Evaluation
- Fluorescein Eye Staining
- Intraocular pressure measurement
- Evaluation of adverse events
- Eye Comfort Index (ILO)
- Adherence Assessment
- Eye symptoms
- Return of the research product
- Return of subject's diary

7.7.4 Security Call

- Evaluation of adverse events

7.7.5 Unscheduled follow-up visits

At the request of the subject or personnel related to the study, unscheduled follow-up visits may be carried out for the reporting of adverse events or any situation that warrants it. During these visits, all pertinent data on the adverse events reported should be collected and, where appropriate, an appropriate management plan should be established.

7.8 Data collection

7.8.1 Source documents

Source documents are all written or printed records derived from automated processes (e.g., printouts of laboratory results issued by automated analysis equipment) where the information is recorded for the first time and which is part of the permanent records of the subject's history. Examples of source documents are the medical history, clinical evolution notes, laboratory reports, cabinet study reports, nursing notes, follow-up notes, surgery records, etc.

The PI is obliged to accept the monitoring of the information related to the study, audits, review by ethics and research committees, and inspections by the health authority, this obligation implies direct access to the source documents.

7.8.2 Electronic forms of data collection

All data related to the protocol will be captured through an electronic *Case Report Form* (eCRF) by the investigation team staff. The data related to the protocol should NOT be captured directly in the eCRF, but should be transcribed from the corresponding source document. This procedure allows monitoring to verify the information captured in the eCRFs. It is the responsibility of the researcher to ensure that the information is transcribed into the eCRFs in a correct, complete, and timely manner. It is understood that all data captured and sent by the eCRF to data analysis is approved by the Researcher.

7.8.3 Archiving

The data collected in this database is anonymous (it only stores the subject number together with other information of interest). The program used for data capture and storage covers the traceability requirements necessary for the execution of clinical studies. The data collected will be stored by the sponsor or the clinical research organization designated for this purpose and its storage will have a duration of 10 years. The master file will remain in the participating institutions in charge of the PI or its work team and must be safeguarded for at least 5 years.

8. Evaluation and management of adverse events

8.1 Regulation and regulations on adverse events

The registration and reporting of adverse events will be carried out in accordance with the guidelines established in NOM-220-SSA1-2016 and the international guidelines ICH E6. [33][47][48][49]

8.2 Definition of Adverse Event

According to the International Council on Harmonization (ICH), an adverse event (AE) is any unfavorable medical appearance in a clinical investigational subject who is administered a pharmaceutical product, regardless of causal attribution. [47] [48] [49]

Therefore, an AE can be any of the following: any unfavorable and unintentional disease, symptom, or sign (including an abnormal laboratory finding) that is temporally related to the use of a medical product, whether or not it is considered related to such a product; any new illness or exacerbation of an existing disease (worsening of the nature, frequency, or severity of a known condition); relapse of an intermittent medical condition (e.g., headache) not present at baseline; any deterioration in a laboratory value or other clinical test (e.g., electrocardiogram [ECG], x-ray) that is related to symptoms or that results in a change in study treatment or concomitant treatment or discontinuation of study medication. [47] [48] [49]

As defined in the previous paragraph, an adverse event is defined as any event that occurs during treatment with a drug or device. However, the definition can also be applied as any unwanted event that occurs during a clinical trial, including behavioral disorders. [49]

8.3 Use of adverse events as a study safety variable

Measuring the safety of the use of PRO-231 is paramount to the study, therefore, it is considered important to report any unwanted manifestations or diseases that occur during the course of the study, regardless of whether or not the manifestation is considered to be related to the treatment under investigation. [49]

8.4 Definitions relevant to the classification of adverse events

Severity (serious/non-serious), also called seriousness (serious/non-serious). Serious or serious is defined as any event that: results in death, threatens life, requires hospitalization or prolongs hospitalization, is a cause of permanent or significant disability or disability, is the cause of alterations or malformations in the newborn, other medically important conditions (Medically important event

or reaction: That clinical manifestation or adverse event that in the opinion of the doctor may not be immediately life-threatening, result in death or hospitalization, but which could endanger the subject or require medical intervention to prevent the occurrence of any of the criteria listed in the definition of serious adverse reaction). [50]

Severity (mild, moderate, or severe). Mild are those that present with minimal symptoms, do not require treatment or suspension of the medication; moderate, when they interfere with usual activities, without threatening the subject's life, require treatment and may or may not require discontinuation of the medication; severe, those that interfere with usual activities and require pharmacological treatment and discontinuation of the medication. [33][47][48]

Causality. It is the relationship that is assigned between the pharmaceutical product and the adverse event: certainly caused by the pharmaceutical product, there is clear evidence of causality, i.e. the adverse event reappears with the administration of the pharmaceutical product; probably caused by the pharmaceutical product, there is a high suspicion of causality but no direct evidence is available or it is considered unnecessary or dangerous, i.e. the reaction disappears when the pharmaceutical product is discontinued; possibly caused by the pharmaceutical, there is additional information to suggest that the cause may be due to another pharmaceuticals or disease; unlikely to be caused by the pharmaceutical product, there is a clear explanation of the origin due to the underlying disease or the use of another pharmaceutical product; conditional, there is a lack of data to issue a clear causality; non-classifiable, those for which once all possible information has been obtained about the adverse event, it remains unclassifiable. [33] [47] [48] [49]

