- Have unresolved injuries or trauma at the time of study entry.
- Having undergone surgical, non-ophthalmologic procedures within the past 3 months.
- Have received doses of vaccine against the Influenza virus or Coronavirus, 7 days prior to the inclusion of this study, or plan to receive it during the study intervention.
- Be or have an immediate family member (e.g., spouse, parent/legal guardian, sibling, or child) who is employed by the research site or sponsor, and who is directly involved in this study.
- Positive smoking (specified as cigarette smoking regardless of quantity and frequency, 4 weeks prior to study inclusion and during the study intervention period).
- Positive alcoholism (specified as the consumption of alcoholic beverages, regardless of quantity and frequency, 72 hours prior to the inclusion of the study and during the study intervention period).

Elimination criteria:

- Withdrawal of the informed consent form.
- Presentation of serious adverse event, whether or not related to the interventions, that, in the judgment of the Principal Investigator (PI) and/or sponsor, could affect the patient's ability to safely continue with study procedures.
- Non-tolerability or hypersensitivity to any of the compounds used during the tests (fluorescein, tetracaine).
- No tolerability or hypersensitivity to any of the investigational drugs.
- Adherence < 80% determined by the subject's diary and corroborated by the final weight of the research products (PI) with respect to the initial weight.

Duration of treatment: 7 days	Duration of the subject in the study: 13 days
Interventions:	

 • Investigational product, dosage, and route of administration: 
 - PRO- 231 . Moxifloxacin 0.5% Ophthalmic Solution. Laboratorios Sophia, S.A. de C.V. Zapopan, Jalisco, Mexico. - Dosage: 1 drop every 6 hours (3 daily applications [TID], in the right eye [OD]). - Route of administration: Topical ophthalmic. • Comparator product, dosage and route of administration: 
 - VIGAMOXI ® Moxifloxacino 0.5% Solución oftálmica. Alcon Laboratories, Inc., Fort Worth, Texas, USA. - Dosage: 1 drop every 6 hours (TID) in OD. - Route of administration: Topical ophthalmic. 	
Evaluation criteria:	

Primary outcome variables:***Safety***

- Incidence of Intervention-Related Unexpected AEs (Time to Assessment [ET]: Days 3, 8, and 12)

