6.1.3 Treatment with the investigational product

The product under investigation will be delivered at the conclusion of the baseline visit. The subject under investigation will begin the application the next day (day 1) by administering one drop every 6 hours, applying a total of one drop three times a day to the right eye during the 7 days of application.

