4. Taking the clinical information collected, either during the care provided at the research center or that provided by the treating physician(s) in the hospital, the PI will record the AE in its clinical note, stating the seriousness, intensity (mild, moderate or severe) and relationship with the investigational product.

5. The PI must migrate the relevant data to the eCRF and its respective adverse event section. By virtue of the fact that, in cases of serious adverse events, the clinical monitor of the study must be notified within 24 hours after learning of it, so that in turn it informs the Clinical Team and the Pharmacovigilance and Technovigilance Unit of Sophia Laboratories (UFTLS), and that the CEI/CI is subsequently notified. Non-serious adverse events will be recorded and treated appropriately and the safety profile of the investigational drug or drug will be reported to the appropriate regulatory authority in the final report of the clinical trial.

The recording of the outcome of the AE depends substantially on the follow-up that the Principal Investigator performs on the subject, since it is expected that most of the harmful phenomena (see subsection 2.5 Risk-benefit assessment and consult the Investigator's Manual) are ophthalmic in nature, however, there may be systemic alterations. Therefore, in the opinion of the researcher, the withdrawal of the participant or their permanence will be considered.

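### The mild, moderate and severe classes in section 8.4 overlap and leave gaps, and read literally an event that starts or worsens after the last dose cannot be severe

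*Combined protocol and SAP*

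**What the plan says.** Section 8.4 gives three classes:

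- Mild: "Mild are those that present with minimal symptoms, do not require treatment or suspension of the medication".
- Moderate: "moderate, when they interfere with usual activities, without threatening the subject's life, require treatment and may or may not require discontinuation of the medication".
- Severe: "severe, those that interfere with usual activities and require pharmacological treatment and discontinuation of the medication".

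Section 8.5.3 has the investigator record each AE, "stating the seriousness, intensity (mild, moderate or severe) and relationship with the investigational product". Section 8.5.2.3 asks for the initial severity of a persistent AE and, if it worsens, its maximum. Table 2 (section 7.4.3) lists severity as a reference value for both the primary AE variable (unexpected, related) and the secondary one (expected, related). Among the tests it gives for those variables is Pearson chi-square or Fisher's exact.

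On timing, the synopsis states "Duration of treatment: 7 days", and section 6.1.3 says "The subject under investigation will begin the application the next day (day 1) by administering one drop every 6 hours". The primary AE variable in the synopsis is "Incidence of Intervention-Related Unexpected AEs (Time to Assessment [ET]: Days 3, 8, and 12", and the timeline puts the safety call at Day 12 ± 1.

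**The concern.** A grade that every event must receive should yield exactly one value per event, and should be usable throughout the period in which events are collected. The 8.4 classes combine how intense an event is with what it requires by way of treatment and discontinuation, and the combinations are not closed. Two investigators, or one investigator on two occasions, could follow the text faithfully and record different grades, or find that none applies. After dosing ends, one of the three conditions for the top class has nothing to act on.

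At stake is the severity breakdown of AEs, which forms part of the description of the two AE variables in a trial whose objective is safety and tolerability. With 19 subjects per arm, moving one subject between classes shifts a subject-level percentage by 1/19 = 5.3 points.

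**Working it through.** **Inputs.** From 8.4: interference with usual activities (I), treatment required (T), discontinuation required (D), and threat to life, which moderate excludes. No figure in the plan bears on this, so there is none to reproduce.

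**Step 1: apply the definitions to every combination.** Take non-life-threatening events. To favour the rule, count absence of interference as minimal symptoms and any treatment as pharmacological. Then mild = no I, no T, no D; moderate = I and T, with D either way; severe = I and T and D.

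| I | T | D | Classes met |
|---|---|---|---|
| no | no | no | mild |
| no | no | yes | none |
| no | yes | no | none |
| no | yes | yes | none |
| yes | no | no | none |
| yes | no | yes | none |
| yes | yes | no | moderate |
| yes | yes | yes | moderate and severe |

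Two combinations give one class, 1 gives two and 5 give none (2 + 1 + 5 = 8). Severe never stands alone, because its conditions contain those of moderate. This is a check of the rule's logic. The cells are not equally likely and are not event frequencies.

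**Step 2: ask whether the empty cells are plausible.** Some are improbable, such as no interference and no treatment but discontinuation required. Others are ordinary. Sections 7.4.4.1, 7.4.4.2, 7.4.4.4 and 7.4.4.5 make certain findings AEs on examination alone: hyperemia of grade 3 or more, chemosis present, loss of 2 or more lines of corrected acuity, and Oxford staining of grade III or more. Such a finding, if treated but not disturbing usual activities, is not mild (treatment) and is neither moderate nor severe (no interference). An event that disturbs activities but needs no treatment also has no class.

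**Step 3: set dosing beside AE collection.** First dose on Day 1, 7 days of dosing: last dosing day = 1 + 7 − 1 = Day 7. AEs are assessed on Days 3, 8 and 12, the last being a call that may fall on Days 11 to 13. For an event with onset or worsening after Day 7, no study medication remains to be discontinued, so on the literal text D = no. In the table, D = no leaves mild, moderate or no class; severe does not occur. If the event also threatens life, interferes with activities and needs treatment, it has no class, since moderate excludes threat to life and severe needs discontinuation.

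**Step 4: limit the result.** An event with onset during dosing that required discontinuation meets severe whenever it is reported, including on Day 8 or at the call. The restriction follows onset or worsening, not the reporting date.

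**The case against.** The strongest reply is that 8.4 speaks of what an event requires. That is a judgement of need, not a record of what was done. A reader might infer that the classes merely log whether the drops were stopped; the text does not support that, and symptoms and interference are the leading criteria. An investigator could also judge that a Day 9 event was of a kind that would have required stopping, and call it severe. That reading is possible, but the plan does not state it, so its use would vary.

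The double class disappears if the highest class met is taken. Section 8.5.2.3 points that way for a persistent event that worsens, but states no general rule. The empty classes remain in either case.

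The consequences are also limited. The primary AE outcome is incidence, and sections 10.3.1 and 10.3.2 name no severity endpoint or severity-based decision. Seriousness has its own definition in 8.4, and the serious-AE criterion in 11.3 rests on that. Efron, Oxford, acuity and Eye Comfort Index measurements capture intensity of the main ocular effects through Day 8 without this rule, though they do not cover other AEs or later days. Section 8.4 also uses the word severity for seriousness, so the Table 2 entry is open to either meaning; sections 8.5.2.3 and 8.5.3 still call for the intensity grade.

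Finally, the classes cite the national pharmacovigilance norm, to which section 8.1 commits AE registration and reporting. Whether the norm prescribes them cannot be told from these documents. That argues against replacing them outright, and the fix respects it.

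**Conclusion.** The point holds in a limited form. The 8.4 classes are neither mutually exclusive nor exhaustive, and on the literal text severe is out of reach for an event that starts or worsens after Day 7. The affected output is the severity tabulation and comparison for the AE variables in Table 2. AE incidence, seriousness and the stopping criterion are untouched.

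Three stronger inferences are not supported. A reader might infer that every AE reported after dosing is capped at moderate; events that required discontinuation during dosing are not. A reader might take the share of follow-up days after Day 7, or the 5 empty cells of 8, as the share of events misgraded; these count calendar days and logical combinations, and the plan gives no expected rate for such events. A reader might infer that the trial's safety conclusion is understated as a whole; the tested outcome is incidence, and most ocular signs have their own scales.

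The conclusion assumes that the three classes are read as written, that suspension in mild and discontinuation in the other two mean the same thing, and that severity in Table 2 means the intensity grade. If the hypothetical reading of the discontinuation condition were written into the plan, the post-dose limit would go, but the gaps would remain.

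**What to change.** For the Table 2 severity analysis, add to 8.4 an intensity grade based only on symptoms and interference with usual activities, worded so that every event falls in exactly one class and so that it applies equally after dosing ends. State in Table 2 that this grade is the severity meant. Record treatment given and action taken with the study product as separate eCRF fields; section 8.5.1 already collects clinical management, dose adjustment and response to removal of the product.

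Keep the present classes as a second field for reports under the cited norm, with a sentence saying that the highest class met applies.

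The cost is protocol wording, a code list and one extra eCRF field. The change concerns classification only; it alters no dose, care or rule for stopping treatment.
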